Urine Albumin and Creatinine:

Low Level Target: **Urine Albumin ~50 mg/L** **Creatinine ~85 mg/dL (~8 mmol/L)**

High Level Target: **Urine Albumin ~180 mg/L** **Creatinine ~220 mg/dL (~20 mmol/L)**

Please note that urine creatinine and Albumin are processed at the same time and can be run in both channels.

Procedure

1. Fill out the requested information (Allegro serial numbers, cartridge lot numbers, QC lot numbers, QC ranges) on the provided Data Sheets (see Appendix).
2. Perform quality control runs on the Allegro being evaluated and the reference analyzer. Record the results for all systems on the Data Sheet and make sure the results are within the manufacturer's control range. **Proceed with testing only if all control results are within range.**
3. Select low, med and high levels of both urine creatinine and Albumin, ideally using discarded random urine collections or, if these are not available, then urine samples that have been spiked with appropriate concentrations of creatinine spiking solution and/or human Albumin (**may need to be tested for homogeneity**).
4. Suggested concentrations for low, medium and high samples: -

	Urine Creatinine	Urine Albumin
Low Target	~25-30 mg/dL (~2.2-2.7mmol/L)	~10-15 mg/L
Medium Target	~200 mg/dL (~18 mmol/L)	~40 mg/L
High Target	~ 400-450 mg/dL (~35-40 mmol/L)	~150-200 mg/L
5. Ensure adequate mixing before analysis.
6. Cartridges are stored at 4° each cartridge requires 10-15 mins warm up time so consider this requirement when planning study needs.
7. Run each Level 10 times on Allegro, consider running only in one channel to reduce variability. Record results on Data Collection Sheet.
8. Total Analysis Time: 7 mins x 10 = 70 mins per level. 210 mins for all levels. Approx. 3.5 hrs plus preparation time.

Data Analysis

The within-run precision of the Allegro be assessed by calculating the % coefficient of variation (%CV) from the mean and standard deviation from the replicate measurements. Acceptability criteria are determined by the medical director and/or institution. Investigators are referred to organizations such as CLSI and the International Standards Organization (ISO) which offer published acceptance criteria [1].

Data Review

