This protocol is recommended and designed by Nova Biomedical to investigate the between-day precision of urine creatinine and urine Albumin measurements on the Allegro system.

Materials Needed

- Nova Biomedical Allegro
- Allegro Kidney Function Cartridges
- Nova Biomedical Allegro Quality Control (QC) Solution
- Reference Analyzer and reagents
- 2mL plastic tubes for decanting urine samples
- Plastic 2mL disposable pipettes
- Full range of adjustable pipettes and tips
- If required appropriate Spiking stock solutions

Important Factors to Consider

Tests: Urine Creatinine and Urine Albumin

Sample Type: Fresh random urine

Sample Size: 25 μ L

Time per UABCR: 7 mins

Linear Range of Operation for Urine Creatinine: 15-500 mg/dL (13.0-44.2 mmol/L)

Linear Range of Operation for Urine Albumin: 3-300 mg/L

Expected Normal Values

Urine Creatinine: For a random urine sample, >12 Years Male 20-370 mg/dL (1.8- 32.7 mmol/L), >12 Years Female 20 – 320 mg/dL (1.8-28.3 mmol/L)

Urine Albumin: For a random urine sample, normal values are typically 0 to 30 mg/dL

Control Levels:

The Allegro supports two levels of controls. The following are suggested ranges for each parameter and level:

Urine Albumin and Creatinine:

Low Level Target: **Urine Albumin ~50 mg/L** **Creatinine ~85 mg/L (~8 mmol/L)**

High Level Target: **Urine Albumin ~180 mg/L** **Creatinine ~220 mg/L (~20 mmol/L)**

Please note that urine creatinine and urine Albumin are processed at the same time

Procedure

1. Fill out the requested information (Allegro serial numbers, cartridge lot numbers, QC lot numbers, QC ranges) on the provided Data Sheets (see Appendix).
2. Perform quality control runs on the Allegro being evaluated and the reference analyzer. Analyse controls on Allegro every day that testing is carried out, 2 runs per day would be performed one in the morning and the other in the afternoon so QC would need to be performed prior to each run, make sure results are within specification before proceeding. Record the results for all systems on the Data Sheet and make sure the results are within the manufacturer's control range. **Proceed with testing only if all control results are within range.**

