3. Select low, med and high levels of both urine creatinine and Albumin. These can be obtained from one or more of the following: a) samples from random urine collections, b) samples spiked with stock concentrations of Albumin and/or creatinine, or c) samples used for the within day precision test. Forty aliquots must be prepared from each sample and frozen.
4. A freshly thawed aliquot will then be analysed every morning and afternoon in duplicate for 10 consecutive working days
5. Suggested concentrations for low, medium and high samples: -

	Urine Creatinine	Urine Albumin
Low Target	~25-30 mg/dL (~2.2-2.7 mmol/L)	~10-15 mg/L
Medium Target	~200 mg/dL (~18 mmol/L)	~40 mg/L
High Target	~ 400-450 mg/dL (~35-40 mmol/L)	~150-200 mg/L
6. Ensure adequate mixing before analysis.
7. Cartridges are stored at 4° each cartridge requires 10-15 mins warm up time so consider this requirement when planning study needs.
8. Run each level in duplicate on the Allegro using the same channel to reduce variability
9. Collect, review and collate data
10. Total Analysis Time: 7 mins x 6 = 42 mins in morning, 7 mins x 6 = 42 mins in afternoon plus preparation time

Data Analysis

The between-day precision of the Allegro be assessed by calculating the % coefficient of variation (%CV) from the mean and standard deviation from the replicate measurements. Acceptability criteria are determined by the medical director and/or institution. Investigators are referred to organizations such as CLSI and the International Standards Organization (ISO) which offer published acceptance criteria [1, 2].

Data Review

This data will be summarized in a final report which will also include an assessment of the accuracy. This report should be reviewed by the study site principal investigator. Results of this laboratory evaluation can be used to document verification of Allegro performance prior to the conductance of clinical studies.

References

1. Clinical & Laboratory Standards Institute (CLSI). *Evaluation of Precision Performance of Quantitative Measurement Methods; Approved Guideline – Second Edition*. EP5-A2.

Appendix 2

Between-Day Precision Study Data Collection Sheet

Hospital Name: _____ Date of Study: _____

System Operator(s): _____

Reference Analyzer _____

Level 1 Urine Creatinine and Urine Albumin

Morning

Reference Analyzer Result: Urine Creatinine mg/dL or mmol/L _____

Reference Analyzer Result: Urine Albumin mg/L or g/L _____

Afternoon

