77						
78						
79						
80						
81						
82						
83						
84						
85						
86						
87						
88						
89						
90						
91						
92						
93						
94						
95						
96						
97						
98						
99						
100						

Name of Person Collecting Data: _____
Signature of Person Collecting Data: _____
Date: _____

1. Urine Creatinine and Urine Albumin Summary Report Template

Urine Creatinine and Urine Albumin Summary Report

Date:

Report Author:

Study Site:

Study Site Principal Investigator/Department:

Materials and Methods

See Protocols I-IV. *Any deviations from protocol should be noted here.*

Summary of Results

I. Precision Studies

Table 1. Urine Creatinine Within-Day Precision for Allegro

	Low Urine Creat	Mid Urine Creat	High Urine Creat
Mean mg/dL or mmol/L			
Standard Deviation			
%CV			
N			
Matrix: Urine			

Table 2. Urine Albumin Within-Day Precision for Allegro

	Low Urine Urine Albumin	Mid Urine Urine Albumin	High Urine Urine Albumin
Mean mg/L or g/L			
Standard Deviation			
%CV			
N			
Matrix: Urine			

Table 3. **Urine Creatinine Between-Day** Precision for Allegro

	Low Urine Creat	Mid Urine Creat	High Urine Creat
Mean mg/dL or mmol/L			
Standard Deviation			
%CV			
N			
Matrix: Urine			

Table 4. **Urine Albumin Between-Day** Precision for Allegro

	Low Urine Urine Albumin	Mid Urine Urine Albumin	High Urine Urine Albumin
Mean mg/L or g/L			
Standard Deviation			
%CV			
N			
Matrix: Urine			

II. Method Comparison

Table 7. **Summary of Linear Regression Analysis Results** Urine creatinine and Urine Albumin for the Allegro

	Urine Creat	Urine Albumin
Slope		
y-intercept (mg/dL)		
R ²		
N		
Urine Creat Range mg/dL or mmol/L		
Urine Albumin Range mg/L or g/L		

Table 8. Summary of Bland-Altman Results

	Urine Creat	Urine Albumin
--	-------------	---------------

Mean Bias (mg/dL)		
95% Limits of Agreement		
Lower		
Upper		
Urine Creat Range mg/dL or mmol/L		
Urine Albumin Range mg/L or g/L		

Summary Findings

Allegro demonstrated

This report has been reviewed and approved by:

Signature of Study Site Principal Investigator

Date

Signature of MASA Director

Date

2. HbA1c

I. Within Day Precision Study Protocol

Protocol based on:

Clinical & Laboratory Standards Institute (CLSI). *Evaluation of Precision Performance of Quantitative Measurement Methods; Approved Guideline – Second Edition*. EP5-A2.

Purpose

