1. Clinical & Laboratory Standards Institute (CLSI). *Method Comparison and Bias Estimation Using Patient Samples; Approved Guideline – Second Edition. EP9-A2.*

Appendix 4

Method Comparison Data Collection Sheet (Case Report Form)

Study Site: _____ Date of Study: _____

System Operator(s): _____

Specimen Type (Venous EDTA Whole Blood) _____

Reference Analyzer _____

	System Name		
	System Serial #		
	Cartridge Lot #		
Low QC	Range:		
High QC	Range:		
Specimen ID	Reference Analyzer Result % or mmol/mol	HbA1c result % or mmol/mol	HbA1c result % or mmol/mol
1			
2			
3			
4			
5			
6			
7			
8			
9			
10			
11			
12			
13			
14			
15			
16			
17			
18			
19			
20			
21			
22			
23			
24			
25			
26			
27			
28			
29			
30			

Specimen ID	System Name		
	System Serial #		
	Cart Lot #		
	Reference Analyzer Result % or mmol/mol	HbA1c result % or mmol/mol	HbA1c result % or mmol/mol
31			
32			
33			
34			
35			
36			
37			
38			
39			
40			
41			
42			
43			
44			
45			
46			
47			
48			
48			
49			
50			
51			
52			
53			
54			
55			
56			
57			
58			
59			
60			
61			
62			
63			
64			
65			
66			
67			
68			
69			
70			
71			
72			
73			

	System Name		
	System Serial #		
	Cart Lot #		
Specimen ID	Reference Analyzer Result % or mmol/mol	HbA1c result % or mmol/mol	HbA1c result % or mmol/mol
74			
75			
76			
77			
78			
79			
80			
81			
82			
83			
84			
85			
86			
87			
88			
89			
90			
91			
92			
93			
94			
95			
96			
97			
98			
99			
100			

Name of Person Collecting Data: _____

Signature of Person Collecting Data: _____

Date: _____

2. HbA1c

Summary Report Template

HbA1c Summary Report

Date:

Report Author:

Study Site:

Study Site Principal Investigator/Department:

Materials and Methods

See Protocols I-IV. *Any deviations from protocol should be noted here.*

Summary of Results

I. Precision Studies

Table 1. **HbA1c Within-Day** Precision for Allegro

	Low HbA1c	Mid HbA1c	High HbA1c
Mean % or mol/mol			
Standard Deviation			
%CV			
N			
Matrix			

Table 2. **HbA1c Between-Day** Precision for Allegro

	Low HbA1c	Mid HbA1c	High HbA1c
Mean % or mol/mol			
Standard Deviation			
%CV			
N			
Matrix			

II. Method Comparison

Table 5. Summary of Linear Regression Analysis Results HbA1C for Allegro

HbA1c	
Slope	
y-intercept (% or mmol/mol)	
R ²	
N	
HbA1c Range % or mmol/mol	

Table 6. Summary of Bland-Altman Results

HbA1c	
Mean Bias (% or mmol/mol)	
95% Limits of Agreement	
Lower	
Upper	
HbA1c (% or mmol/mol)	

Summary Findings

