60									
61									
62									
63									
64									
65									

66									
67									
68									
69									

Method Comparison Data Collection Sheet (Case Report Form)

Specimen ID	System Name								
	System Serial #								
	Cart Lot #								
	Total Chol mg/dL or mmol/L	Total Chol mg/dL or mmol/L	Reference Analyzer Result Total Chol (mg/dL or mmol/L)	Trigs mg/dL or mmol/L	Trigs mg/dL/ or mmol/L	Reference Analyzer Result Trig (mg/dL or mmol/L)	HDL Chol mg/dL or mmol/L	HDL Chol mg/dL or mmol/L	Reference Analyzer Result HDL Chol(mg/dL or mmol/L)
70									
71									
72									
73									
74									
75									
76									
77									
78									
79									
80									
81									
82									
83									
84									
85									
86									
87									
88									
89									
90									
91									
92									
93									
94									
95									
96									
97									
98									
99									
100									

Name of Person Collecting Data: _____
 Signature of Person Collecting Data: _____
 Date: _____

3. Total Cholesterol, Triglyceride and HDL Cholesterol

Summary Report Template

Total Cholesterol, Triglyceride and HDL Cholesterol Summary Report

Date:

Report Author:

Study Site:

Study Site Principal Investigator/Department:

Materials and Methods

See Protocols I-IV. *Any deviations from protocol should be noted here.*

Summary of Results

I. Precision Studies

Table 1. Total Cholesterol Within-Day Precision for Allegro

	Low Cholesterol	Mid Cholesterol	High Cholesterol
Mean mg/dL or mmol/L			
Standard Deviation			
%CV			
N			
Matrix			

Table 2. Triglyceride Within-Day Precision for Allegro

	Low Triglyceride	Mid Triglyceride	High Triglyceride
Mean mg/dL or mmol/L			
Standard Deviation			
%CV			
N			
Matrix			

Table 3. HDL Cholesterol Within-Day Precision for Allegro

	Low Cholesterol	Mid Cholesterol	High Cholesterol
Mean (mg/dL)			
Standard Deviation			
%CV			
N			
Matrix			

Table 4. Total Cholesterol Between-Day Precision for Allegro

	Low Cholesterol	Mid Cholesterol	High Cholesterol
Mean (mg/dL)			
Standard Deviation			
%CV			
N			
Matrix			

Table 5. Triglyceride Between-Day Precision for Allegro

	Low Triglyceride	Mid Triglyceride	High Triglyceride
Mean (mg/dL)			
Standard Deviation			
%CV			
N			
Matrix			

Table 6. HDL Cholesterol Between-Day Precision for Allegro

	Low HDL Chol	Mid HDL Chol	High HDL Chol
Mean (mg/dL)			
Standard Deviation			
%CV			
N			
Matrix			

III. Method Comparison

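### The between-day %CV measures roughly total within-laboratory imprecision, not day-to-day variation, so its label does not match the figure

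*Protocol*

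**What the plan says.** The sentence under Data Analysis is identical for urine creatinine and albumin (1.II), HbA1c (2.II) and lipids (3.II): "The between-day precision of the Allegro be assessed by calculating the % coefficient of variation (%CV) from the mean and standard deviation". It ends by taking the "standard deviation from the replicate measurements", without saying which results those are.

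The procedure in each section is nested. Step 2 states that "2 runs per day would be performed one in the morning and the other in the afternoon", and step 4 has each level "analysed every morning and afternoon in duplicate for 10 consecutive working days".

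The summary report templates carry the result in tables such as "Urine Creatinine Between-Day" (Kidney, Table 3), "HbA1c Between-Day" (HbA1c, Table 2) and "Total Cholesterol Between-Day Precision for Allegro" (Lipid, Table 4). Each gives one mean, SD, %CV and N per level, with no row for a variance component.

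The companion within-day study has the instruction "Run each Level 10 times on Allegro". Its own Data Analysis text (1.I, 2.I, 3.I) calls the result within-run precision, while its report tables call it within-day.

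**The concern.** The Scope section lists within-day and between-day precision as separate components of the assessment for every profile. A reader will therefore take the between-day table as showing how far results move from one day to the next. A single SD over nested data cannot show that. It mixes replicate noise, morning-to-afternoon variation and day variation, with replicate noise at full weight.

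Three things are at stake:

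- An analyser that is stable across days still receives a non-zero between-day CV. A medical director who compares that figure with a limit meant for day-to-day variation could fault the device for its repeatability alone.
- Morning-to-afternoon variation, which the two-run design could reveal, is inside the figure but not shown.
- Because the rule does not say which results enter the SD, two sites could obtain different figures from the same data.

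**Working it through.** **Inputs from the Protocol.** There are 10 days, 2 runs per day and 2 replicates per run (Procedure, steps 2 and 4). This gives 10 × 2 × 2 = 40 results per level, which matches the forty aliquots in 1.II if each result uses its own aliquot. The stated session times also fit duplicates of every level:

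- urine: 3 levels × 2 × 7 min = 42 min
- HbA1c: 2 × 2 × 6.25 min = 25 min
- lipids: 2 × 2 × 10 min = 40 min

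**Input not in the Protocol.** No component SDs are given, so the CVs below are assumptions that span a range.

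**Reading A: SD of all 40 results.** Let Ve, Vrun and Vday be the replicate, run-within-day and day variances. The expected sums of squares are:

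- day (9 df): 9 × (Ve + 2 Vrun + 4 Vday)
- run within day (10 df): 10 × (Ve + 2 Vrun)
- replicate (20 df): 20 × Ve

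Their sum is 39 Ve + 38 Vrun + 36 Vday. Dividing by 39 gives Ve + 0.974 Vrun + 0.923 Vday. Total within-laboratory variance is Ve + Vrun + Vday, so the pooled SD is between √0.923 = 96.1% and 100% of the total SD, whatever the components are.

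**Reading B: SD of the 10 day means.** The expected variance is Vday + Vrun/2 + Ve/4.

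**Worked case, CVs of 4% (repeatability), 1.5% (run) and 2% (day):**

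- A: 16 + 0.974 × 2.25 + 0.923 × 4 = 21.88, so CV 4.68%. Repeatability is 16/21.88 = 73% of this variance.
- B: 4 + 1.125 + 4 = 9.125, so CV 3.02%.
- Total: 16 + 2.25 + 4 = 22.25, so CV 4.72%.

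| Assumed CV (repeatability, run, day) | A: all 40 | B: day means | Total CV | True day CV | A ÷ day | A ÷ total | Repeatability share of A |
|---|---|---|---|---|---|---|---|
| 4, 0, 0 | 4.00% | 2.00% | 4.00% | 0% | undefined | 100% | 100% |
| 4, 1.5, 2 | 4.68% | 3.02% | 4.72% | 2% | 2.3 | 99% | 73% |
| 3, 1, 3 | 4.28% | 3.43% | 4.36% | 3% | 1.4 | 98% | 49% |
| 2, 1, 4 | 4.44% | 4.18% | 4.58% | 4% | 1.1 | 97% | 20% |

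Simulation with 40,000 data sets per case agrees to within 0.01 percentage points: 3.99, 4.68, 4.28 and 4.45 for A; 2.00, 3.02, 3.43 and 4.19 for B.

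**Can the day component be recovered?** Yes: Vday is estimated by (MS_day − MS_run)/4 and Vrun by (MS_run − MS_replicate)/2. In simulation with other assumed values, the average estimate of Vday was 1.00 for a true 1, 3.99 for a true 4 and 9.00 for a true 9.

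The estimate is imprecise with 10 days. The chance that it is negative, from the F distribution with 9 and 10 df, is 0.505, 0.200, 0.020 and 0.001 for the four rows. In the second row, the day CV estimate with negatives set to zero has a 2.5 to 97.5 percentile range of 0 to 3.8% around a true 2%.

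**The case against.** The best case for the plan is that between-day precision may simply name the study condition, imprecision seen across 10 days. On that usage the pooled CV is a sound total CV and only a word is at issue. It is also said that:

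- the sheets in Appendix 2 head the Day 1 to Day 10 rows as replicates, so the all-40 reading is not certain;
- the N row would reveal which results were used;
- a reader can compare the across-day CV with the within-day CV in the same report;
- acceptability is left to the institution, and the pooled figure errs against the device;
- a day component from 10 days is imprecise;
- such details can wait for a statistical analysis plan.

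Part of this stands. The pooled figure is usable as a total CV, the day component will be imprecise, and N would normally distinguish 40 results from 10 day means.

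The rest does not rescue the rule. The Protocol never defines between-day as total imprecision and lists it beside within-day precision as a separate component. The heading on the data sheets points at most to the day-means reading, which does not isolate the day effect either. The comparison with the within-day CV rests on only 10 replicates. For HbA1c and lipids it also crosses materials, because the between-day study suggests frozen control solution where the within-day study uses whole blood. The Protocol itself fixes both the formula and the report table, so this is a stated rule that does not deliver the quantity on its label, not a detail left for later.

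**Conclusion.** The concern holds and should be fixed. That neither reading gives the day component follows from the design alone and needs no assumed values. On the natural all-40 reading, the reported figure is 96% to 100% of the total within-laboratory SD.

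How far it overstates day-to-day variation depends on components the Protocol does not give. In the assumed cases the overstatement runs from 1.1 times (day variation dominant) to 2.3 times (repeatability dominant), and with no day effect the whole figure is spurious as a between-day CV.

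The calculation assumes a balanced data set and independent random day, run and replicate effects. The fault lies in the label and the missing breakdown. The recorded data are unaffected.

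**What to change.** In 1.II, 2.II and 3.II, replace the analysis sentence with a nested random-effects analysis of variance (day, run within day, replicate within run). For each level, report the repeatability, between-run-within-day, between-day and total within-laboratory CV. State that negative component estimates are set to zero and flagged, and note beside the table that the day component is imprecise with 10 days.

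At minimum, state which results enter the SD and relabel the 40-result figure as total within-laboratory CV. In either case, label the 10-replicate table as repeatability (within-run), in line with the Data Analysis text of 1.I, 2.I and 3.I.

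The cost is one reworded sentence in three sections plus extra rows or new labels in the report tables. No new measurements are needed, because the between-day data sheets already record day, morning or afternoon, and replicate. The price is that the day component will often be estimated as zero: in about half of data sets when there is no day effect, and in about 20% at CVs of 4%, 1.5% and 2%.
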